4.3.4 Clinical Laboratory Tests

A Laboratory Manual will be provided to the sites that specifies the procedures for collection, processing, storage, and shipment of samples, as well as laboratory contact information, specific to this clinical research study.

Clinical laboratory safety tests including serum pregnancy tests will be performed in a central clinical laboratory. In addition to the safety laboratory hematology samples at the central clinical laboratory, a complete blood count with differentials will be performed at the site's local laboratory at Visit 1 (Week -5) and Visit 3 (Week -1). The Visit 3 (Week -1) blood eosinophil count from the local laboratory will be used for stratification.

Urine pregnancy tests may be performed at the site using a licensed test (dipstick). Abnormal laboratory results should be repeated as soon as possible (preferably within 24 to 48 hours).

The following clinical laboratory tests will be performed (see Table 4.2.1-1, Table 4.2.2-1, Table 4.2.2-2, Table 4.2.3-1 for the schedule of tests):

Serum Chemistry

- Calcium
- Chloride
- Potassium
- Sodium
- Bicarbonate
- Aspartate transaminase (AST)
- Alanine transaminase (ALT)
- Albumin

- Uric acid
- Creatinine
- Total bilirubin
- Glucose
- Alkaline phosphatase (ALP)
- Blood urea nitrogen (BUN)
- Total protein

Note for serum chemistries: Tests for AST, ALT, ALP, and total bilirubin must be conducted concurrently and assessed concurrently. In the event that the AST or ALT is elevated $\geq 3 \times \text{ULN}$, creatine kinase will be measured.

Hematology

- White blood cell (WBC) count with differential Platelet count
- Red blood cell (RBC) count
- Hematocrit
- · Hemoglobin

Urinalysis

- Nitrites (dipstick)
- Protein (dipstick)
- Glucose (dipstick)
- Ketones (dipstick)

- Blood (dipstick)
- Bilirubin (dipstick)
- Urine microscopy and urine casts (as required)
- Urine culture (as required)

Pregnancy Test

Serum beta-hCG (at screening only, required of all females)

Urine human chorionic gonadotropin (hCG, required for females of childbearing potential only)

Other Safety Tests

- Hepatitis B surface antigen, hepatitis C antibody (screening only)
- HIV-1 and HIV-2 antibody (screening only)

4.3.4.1 Tuberculosis Testing

All subjects will have the QFT-G test, which will be performed by the central clinical laboratory.

If a subject has an indeterminate QFT-G test at screening, the chest x-ray shows no evidence of active TB, there are no signs or symptoms of active TB, there is no recent contact with

anyone with active TB, and there is no history of latent (unless diagnosed within the 3 years prior to screening with documentation of completion of appropriate treatment) or active TB, the subject may be randomized and will have additional QFT-G testing performed at Weeks 12, 28, 40, and 52. Additionally, if in the opinion of the principal investigator and after discussion with the medical monitor, an expert specializing in TB may be consulted prior to randomization. If, during the study, a subject is determined to have a positive QFT-G result, the local country guidelines should be consulted for acceptable anti-TB treatment regimens. If no local guidelines exist for immunocompromised individuals, then USA guidelines must be followed.

4.3.5 Pharmacokinetic Evaluation and Methods

Blood samples for MEDI9929 concentration determination will be collected prior to administration of investigational product according to the schedule of study procedures. MEDI9929 concentrations in serum will be measured by enzyme-linked immunosorbent assay. Instructions for sample collection, processing, storage, and shipment can be found in a laboratory manual provided to the sites.

4.3.6 Immunogenicity Evaluation and Methods

Serum samples to measure the presence of ADA will be collected prior to administration of investigational product according to the schedule of study procedures. If the subject discontinues the study early and does not agree to return for the 12 weeks of follow-up, an ADA sample will be collected at the EDV (see Section 4.1.6). Confirmed ADA-positive samples will be tested using a neutralizing antibody assay.

Instructions for sample collection, processing, storage, and shipment can be found in a separate laboratory manual provided to the sites.

4.3.7 Biomarker Evaluation and Methods

Serum Biomarkers

Serum will be collected during the study to evaluate changes in biomarkers related to asthma, Th2 inflammation, and the TSLP pathway. Baseline levels of serum biomarkers will also be used to identify predictive biomarkers of MEDI9929 response, including IgE fluorescence enzyme immunoassay for common aeroallergens to identify those with atopic asthma. The specific biomarkers that will be analyzed are cytokines, chemokines and inflammatory mediators associated with asthma and the TSLP pathway.

Flow Cytometry

Whole blood samples will be collected during the study at selected sites to evaluate intracellular cytokines in T cells by flow cytometry following *ex vivo* stimulation by phorbol myristate acetate.

Deoxyribonucleic Acid

Whole blood will be collected at a single timepoint Visit 4 (Week 0, Day 1) after subjects have been randomized into the study for extraction of DNA and analysis of polymorphisms associated with asthma, TSLP or MEDI9929 response. The collection of blood for DNA analysis is optional and subjects who do not wish to have the DNA test done will still be eligible for the study. The completion of a separate informed consent form (ICF) related to DNA is required. Subjects who elect to have the DNA test done may, at any time before the end of the study, request that the blood collected for DNA analysis be destroyed.

4.3.8 Estimate of Volume of Blood to Be Collected

The estimated volume of blood to be collected from each subject at each visit (and across all visits) from screening through the Week 64 is presented in Table 4.3.8-1.

Table 4.3.8-1 Estimated Blood Volume to be Collected by Visit

Visit Week	Visit Number	Estimated Blood Volume (mL)
-5	1	15.0
-3	2	0.0
-1	3	10.0
0	4	40.0 ^{a, b}
2	5	0.0
4	6	25.0
6	7	0.0
8	8	0.0
10	9	0.0
12	10	30.0 ^{b, c}
14	11	0.0
16	12	0.0
18	13	0.0
20	14	25.0
22	15	0.0
24	16	0.0
26	17	0.0

Visit Week Visit Number Estimated Blood Volume (mL) 30.0 b, c 28 18 30 19 0.0 32 20 0.0 34 21 0.0 22 0.0 36 23 0.0 38 40 26.0 24 25 42 0.0 44 0.0 26 27 46 0.0 0.0 48 28 50 29 0.0 30.0 b, c 52 30 58 31 0.0 28.0 b 64 32 259.0 **Total**

Table 4.3.8-1 Estimated Blood Volume to be Collected by Visit

DNA = deoxyribonucleic acid; OFT-G = QuantiFERON tuberculosis Gold

4.4 Study Suspension or Termination

The sponsor reserves the right to temporarily suspend or terminate this study at any time. The reasons for temporarily suspending or terminating the study may include but are not limited to the following:

- 1. The incidence or severity of AEs in this or other studies indicates a potential health hazard to subjects.
- 2. Subject enrollment is unsatisfactory.
- 3. Non-compliance that might significantly jeopardize the validity or integrity of the trial.
- 4. Sponsor decision to terminate development.

If MedImmune determines that temporary suspension or termination of the study is required, MedImmune will discuss the reasons for taking such action with all participating investigators (or head of the medical institution, where applicable). When feasible,

^a This includes 8.5 mL of blood for the optional DNA analysis

b This includes 4 mL of blood for the flow cytometry, which is only being collected at selected study sites

Includes 3-mL sample for QFT-G, which will only be collected from subjects found to have indeterminate QFT-G at screening

MedImmune will provide advance notice to all participating investigators (or head of the medical institution, where applicable) of the impending action.

If the study is suspended or terminated for safety reasons, MedImmune will promptly inform all investigators, heads of the medical institutions (where applicable), and/or institutions conducting the study. MedImmune will also promptly inform the relevant regulatory authorities of the suspension/termination along with the reasons for such action. Where required by applicable regulations, the investigator or head of the medical institution must inform the Institutional Review Board/Independent Ethics Committee (IRB/IEC) promptly and provide the reason(s) for the suspension/termination. If the study is suspended for safety reasons and it is deemed appropriate by the sponsor to resume the study, approval from the relevant regulatory authorities (and IRBs/IECs when applicable) will be obtained prior to resuming the study.

4.5 Investigational Products

4.5.1 Identity of Investigational Products

MedImmune will provide the investigators with investigational products (Table 4.5.1-1) using designated distribution centers.

Table 4.5.1-1 Identification of Investigational Products

Investigational Product	Manufacturer	Concentration and Formulation as Supplied
MEDI9929 (AMG 157)	Amgen	70 mg/mL MEDI9929 formulated with 10 mM sodium acetate, 9% (w/v) sucrose, and 0.004% (w/v) polysorbate 20, pH 5.2
Placebo	Amgen	Placebo contains the same excipients, in the same concentration only lacking MEDI9929

(w/v) = weight by volume

Excipients include sodium acetate, sucrose, and polysorbate 20.

Investigational product will be supplied to the site in open-label kits with 10 vials of either MEDI9929 or placebo. Each kit has a unique number that is printed on all labels within the kit (ie, the outer carton label and the label of each container within the carton).

4.5.1.1 Investigational Product Dose Preparation

Investigational Product Inspection

Each vial should be visually inspected by the unblinded investigational product manager prior to dose preparation. The investigational product will be provided to the study sites as a colorless to slightly yellow clear 1 mL solution (70 mg/mL) contained in 5 mL single use glass vials to be stored frozen at -20°C to -70°C until used.

If there are any defects noted with the investigational product, the investigator and site monitor should be notified immediately. Refer to the Product Complaint section (Section 4.5.1.4) for further instructions.

Dose Preparation Steps

MEDI9929 does not contain preservatives and any unused portion must be discarded. Preparation of MEDI9929 is to be performed aseptically. Total in-use storage time from needle puncture of the investigational product vial to start of administration should not exceed 4 hours at room temperature or 24 hours at 2°C to 8°C. If storage time exceeds these limits, a new dose must be prepared from new vials/syringes.

To prepare the subject's dose, the unblinded investigational product manager will select investigational product for administration according to the kit identification numbers assigned by the IXRS.

Allow the vials to thaw in the dark, at room temperature (20°C to 25°C) for up to 2 hours. Vials should be checked for cracks or damage that may occur if the thawing process is not performed properly. Damaged product should not be administered and the investigator and site monitor should be notified immediately. Refer to the Product Complaint section (Section 4.5.1.4) for further instructions.

Do not disturb the vials during the thaw, except to gently swirl to check for completion of thaw. Do not refreeze the vials once set up for thaw. Never shake vials vigorously, especially during the thawing process.

Five vials of investigational product will be assigned by IXRS for each dose. To prepare the investigational product for administration, the unblinded investigational product manager should remove the tab portion of the vial cap and clear the stopper with 70% ethyl alcohol or equivalent. Assigned vials should be used at one time to prepare the dose required at each

Template 16.0

visit. Unused product in opened and dispensed vials should not be used for subsequent dosing and should be stored for investigational product accountability.

Doses of investigational product will be administered by 3 injections (see Table 3.1.2-1) and must be prepared using plastic disposable syringes and aseptic technique by the unblinded investigational product manager/unblinded study personnel as presented in Table 4.5.1.1-1. Each syringe will be numbered by the unblinded investigational product manager in the order they are prepared. The 1-mL syringe will always be No. 1.

Table 4.5.1.1-1 Dose Preparation

Treatment Arm	Dose	Dose Preparation Instruction	Syringe
1	Placebo 5 vials placebo	Step 1: Withdraw 1 mL of placebo using a 1-mL syringe with a 19-gauge needle Remove the 19-gauge needle Replace with a 27-gauge 1/2-inch needle and cap until administration Label syringe as No. 1	1 mL
		Step 2: Withdraw 0.5 mL of placebo using a 3-mL syringe with a 19-gauge needle Remove the 19-gauge needle Replace with another 19-gauge needle and cap Set vial aside	
		Step 3: With the same syringe used in Step 2, withdraw 1 mL of placebo for a total volume of 1.5 mL Remove the 19-gauge needle Replace with a 27-gauge 1/2-inch needle and cap syringe until administration Label syringe as No. 2	3 mL
		Step 4: Repeat Steps 2 and 3 for remaining 2 placebo vials Label syringe as No. 3	3 mL
2		Step 1: Withdraw 1 mL of MEDI9929 using a 1-mL syringe with a 19-gauge needle Remove the 19-gauge needle Replace with a 27-gauge 1/2-inch needle and cap until administration Label syringe as No. 1	1 mL
	70 mg 1 vial MEDI9929 4 vials placebo	Step 2: Withdraw 0.5 mL of placebo using a 3-mL syringe with a 19-gauge needle Remove the 19-gauge needle Replace with another 19-gauge needle and cap Set vial aside Step 3: With the same syringe used in Step 2, withdraw 1 mL of	3 mL
		placebo for a total volume of 1.5 mL Remove the 19-gauge needle Replace with a 27-gauge 1/2-inch needle and cap syringe until administration Label syringe as No. 2	

Table 4.5.1.1-1 Dose Preparation

Treatment Arm	Dose	Dose Preparation Instruction	
		Step 4: Repeat Steps 2 and 3 for remaining 2 placebo vials Label syringe as No. 3	3 mL
3	210 mg 3 vials MEDI9929 2 vials placebo	Step 1: Withdraw 1 mL of MEDI9929 using a 1-mL syringe with a 19-gauge needle Remove the 19-gauge needle Replace with a 27-gauge 1/2-inch needle and cap syringe until administration Label syringe as No. 1	1 mL
		Step 2: Withdraw 0.5 mL of placebo using a 3-mL syringe with a 19-gauge needle Remove the 19-gauge needle Replace with another 19-gauge needle and cap Set vial aside	3 mL
		Step 3: With the same syringe used in Step 2, withdraw 1 mL of MEDI9929 for a total volume of 1.5 mL Remove the 19-gauge needle Replace with a 27-gauge 1/2-inch needle and cap syringe until administration	
		Label syringe as No. 2 Step 4: Repeat Steps 2 and 3 for remaining one placebo vial and one MEDI9929 vial Label syringe as No. 3	3 mL
4	280 mg 5 MEDI9929 vials	Step 1: Withdraw 1 mL of MEDI9929 using a 1-mL syringe with a 19-gauge needle Remove the 19-gauge needle Replace with a 27-gauge 1/2-inch needle and cap syringe until administration Label syringe as No. 1	1 mL
		Step 2: Withdraw 0.5 mL of MEDI9929 using a 3-mL syringe with a 19-gaugeG needle Remove the 19-gauge needle Replace with another 19-gauge needle and cap Set vial aside	
		Step 3: With the same syringe used in Step 2, withdraw 1 mL of MEDI9929 for a total volume of 1.5 mL Remove the 19-gauge needle Replace with a 27-gauge 1/2-inch needle and cap syringe until administration Label syringe as No. 2	3 mL
		Step 4: Repeat Steps 2 and 3 for remaining 2 MEDI9929 vials Label syringe as No. 3	3 mL

Note: Used vials should not be discarded. These will be kept for investigational product accountability.

4.5.1.2 Treatment Administration

The first day of dosing is considered Day 1. The investigational product will be administered with 3 (2×1.5 mL and 1×1 mL) SC injections Q2W.

The investigational product will be administered by blinded site personnel via a 27-gauge 1/2-inch needle. The person administering the dose will wipe the skin surface of the administration sites with alcohol and allow to air dry. The skin will be pinched to isolate the SC tissue from the muscle. The needle will be inserted at a 90-degree angle approximately halfway into the SC tissue. The investigational product will be slowly injected (at least 5-second duration is recommended) into the SC tissue using gentle pressure. The area should not be massaged after injection.

The 3 required injections should be administered using separate injection sites on the anterior thigh, abdomen, or upper arm. Injections administered in the same location should be at least 1-inch apart. The upper arm should only be used for the smaller volume (1 mL) injections. Subjects who have a history of mastectomy with lymph node dissection should not have any study medication administered in the affected arm.

If any of the following should occur, the investigator should reschedule the visit and investigational product should not be administered:

- The subject received allergen immunotherapy injection on the same day as scheduled investigational product administration
- The subject has an intercurrent illness that in the opinion of the investigator and/or medical monitor may compromise the safety of the subject in the study (eg, viral illnesses)
- The subject, in the opinion of the investigator, is experiencing an acute or emerging asthma exacerbation
- The subject is febrile (≥ 38°C; ≥ 100.4°F) within 72 hours prior to investigational product administration

If the subject reports an injection site reaction, the investigator or qualified designee will complete the AE eCRF page and an additional eCRF page with questions about the injection site reaction.

Rotation of Injection Sites

It is advised that the site of injection be rotated and the subject gets investigational product injections in different anatomical sites at each treatment visit. Suggested scheme of the

injection site rotation is shown in Figure 4.5.1.2-1. For ease or tracking injection sites, suggested investigational product administration locations for one study visit may be: one injection in right upper arm, one injection in right abdomen, and one injection in right anterior thigh. Each syringe number and corresponding injection site must be documented on the eCRF and in the source documents (eg, syringe No. 1 upper arm [Site 1 or 4], syringe No. 2 abdomen [Site 2 or 5], syringe No. 3 anterior thigh [Site 3 or 6]) at each treatment visit.

[figure not shown]

Figure 4.5.1.2-1 Rotation of Injection Sites

In cases when rotation of the injection site is not feasible and/or the subject prefers not to rotate injection sites, the reason for not rotating the injection site should be documented in the source documents.

4.5.1.3 Monitoring of Dose Administration

For the first 2 doses of investigational product, subjects will remain at site for a minimum of 2 hours or until stable, whichever is later. For the third and subsequent doses of investigational product, subjects will remain at site a minimum of 1 hour or until stable, whichever is later. Discharge from site will be determined by the investigator.

Vital signs (blood pressure, temperature, pulse rate, and respiration rate) will be obtained before investigational product administration on all treatment visits. After investigational

product administration, subjects will be monitored for immediate drug reactions; vital signs will be taken 60 and 120 minutes (± 5 minutes) after the first 2 doses of investigational product are administered, and 60 minutes (± 5 minutes) after the third and subsequent doses of investigational product are administered. If the subject is not stable, vital signs should be monitored at least hourly until the subject is discharged from the study center.

As with any antibody, allergic reactions to dose administration are possible. The World Health Organization has categorized anaphylaxis into 2 subgroups, which are clinically indistinguishable: immunologic (IgE-mediated and non-IgE-mediated [eg, IgG and immune complex mediated]) and nonimmunologic (Johansson et al, 2004). The clinical criteria for defining anaphylaxis for this study are listed in Appendix 2. A guide to the signs and symptoms and management of acute anaphylaxis is provided in Appendix 3. Appropriate drugs, such as epinephrine, antihistamines, corticosteroids, etc, and medical equipment to treat anaphylactic reactions must be immediately available at study sites, and study personnel should be trained to recognize and treat anaphylaxis according to local guidelines.

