1.5 Rationale for Conducting the Study

Efficacy results from the inhaled allergen challenge clinical study (Study 20101183) suggest that MEDI9929 is pharmacologically active in subjects with asthma. Since there is a medical need for new therapies to reduce the number and severity of asthma exacerbations and to improve asthma control in patients with severe asthma who are unable to gain complete asthma control using currently available therapies (eg, ICS and LABA combinations together with additional controller therapies), a Phase 2 clinical study is being conducted to evaluate

the efficacy of 3 dose levels of MEDI9929 in this target population. The information gained from this study will have significant value in determining whether MEDI9929 has the potential to be developed as therapy for these patients. Results from this study will also form the basis for decisions for design for future studies.

Clinical and nonclinical experience with MEDI9929 demonstrates no safety or tolerability concerns to date. Potential risks based on the mechanism of action of MEDI9929 include immune complex disease, serious infections, and hypersensitivity and allergic reactions. Risk minimization strategies associated with MEDI9929 have been identified and are described in the current Investigator's Brochure and are included in the protocol. Additional risks associated with the conduct of the study (eg, collection of blood for safety, pharmacokinetics (PK), and pharmacodynamic (PD) assessments and spirometry testing) do not have a significant impact on the study. Given that appropriate measures have been instituted in this study to protect subjects from the possible risks, the results of the inhaled allergen challenge clinical study, and the unmet medical need for the target population, the current risk-benefit profile appears favorable and justifies the administration of MEDI9929 in this study.

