An ECG sub-study will be done in subgroup of subjects to confirm that MEDI9929 does not affect cardiac electrophysiological intervals. Additionally, flow cytometry will be performed at selected sites to evaluate intracellular cytokines in T cells by flow cytometry following *ex vivo* stimulation by phorbol myristate acetate.

Subjects will be in this study for approximately 1.3 years (69 weeks), which includes a screening/run-in period of up to approximately 5 weeks, a 52-week treatment period, and a 12-week post-treatment follow-up period. The last dose of investigational product will be administered at Week 50.

Investigational Product administered to all subjects Q2W

Figure 3.1.1-1 Study Flow Diagram

BD = bronchodilator; EOS = eosinophils; FEV₁ = forced expiratory volume in 1 second; ICS = inhaled corticosteroids; N = number of subjects per treatment group; Q2W = every 2 weeks; Q4W = every 4 weeks, SC = subcutaneous

Note: Every subject receives 3 injections of investigational product Q2W (subjects receiving MEDI9929 Q4W will receive placebo on alternate weeks in order to maintain the blind) in the study. All subjects will be on background asthma therapy of medium- or high-dose ICS and LABA with or without additional asthma controller medications (LTRA, LAMA, cromones, theophylline, and/or maintenance OCS) from screening through the follow-up period.

The endpoints to be measured in this study are described in Section 2.2.

^{*} Current post-BD FEV $_1$ reversibility is defined as post-BD change in FEV $_1$ of $\geq 12\%$ and ≥ 200 mL at one of the screening visits

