3.1.2 Treatment Regimen

Approximately 552 subjects will be randomized in a 1:1:1:1 ratio to receive one of 3 SC dose levels of MEDI9929 or SC placebo for 52 weeks as described in Table 3.1.2-1. All subjects will receive 3 injections (2×1.5 mL and 1×1.0 mL) Q2W in order to maintain the blinding of the different doses

Table 3.1.2-1 Investigational Product Dose and Treatment Regimen

Treatment Arm	N	Dose	Treatment Regimen		
1	1 138 Placebo		3 SC injections Q2W from Week 0, Day 1 to Week 50		
			• 1 × 1 mL placebo and 2 × 1.5 mL placebo		
			3 SC injections Q4W from Week 0, Day 1 to Week 48		
	138	70 mg	• 1×1 mL MEDI9929 and 2×1.5 mL placebo		
2	2 138 70 mg		3 SC injections Q4W from Week 2 to Week 50		
			• 1×1 mL placebo and 2×1.5 mL placebo		
3 SC injections Q4W from Week 0, Day 1 to Week 48		3 SC injections Q4W from Week 0, Day 1 to Week 48			
3 138 210 mg 0.5 mL placebo in each sys			• 1×1 mL MEDI9929 and 2×1.5 mL (combining 1 mL MEDI9929 and		
		210 mg	0.5 mL placebo in each syringe)		
		3 SC injections Q4W from Week 2 to Week 50			
			• 1 × 1 mL placebo and 2 × 1.5 mL placebo		
4	138	280 mg	3 SC injections Q2W from Week 0, Day 1 to Week 50		
7	4 138 280 Hig		• 1× 1 mL MEDI9929 and 2 × 1.5 mL MEDI9929		

N = number of subjects in each treatment group; Q2W = every 2 weeks; Q4W = every 4 weeks; SC = subcutaneous

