4 MATERIALS AND METHODS

4.1 Subjects

4.1.1 Number of Subjects

Approximately 552 subjects will be randomized in a 1:1:1:1 ratio to receive one of 3 doses of MEDI9929 or placebo. Approximately 138 subjects will be randomized to each treatment arm.

Subjects will be stratified as described in Section 3.1.1. The target enrollment for each stratification factor is as follows:

- Study sites (non-Japanese or Japanese) Japanese population will account for approximately 15% of the targeted enrollment of 552 subjects.
- Blood eosinophil count at least 50% of all subjects randomized will have blood eosinophil count ≥ 250 cells/μL.
- ICS dose level at least 40% of all subjects randomized will be taking high-dose ICS and/or maintenance OCS.

In addition to the target enrollment for each stratification factor, at least 50% of subjects in the study will demonstrate current post-BD FEV₁ reversibility.

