4.6 Treatment Assignment and Blinding

4.6.1 Methods for Assigning Treatment Groups

An IXRS will be used for randomization to a treatment group and assignment of blinded investigational product kit numbers.

A subject is considered randomized into the study when the investigator or designee notifies the IXRS that the subject meets eligibility criteria and the IXRS provides the assignment of blinded investigational product kit numbers to the subject.

Prior to randomization, subjects will be stratified by study site (non-Japanese and Japanese), then subjects will be stratified by blood eosinophil count (\geq or < 250 cells/ μ L) and by ICS dose level (medium or high). Subjects taking maintenance OCS will be automatically assigned to the high-dose ICS strata. There will be a total of 8 strata; 4 strata for non-Japanese subjects and 4 identical strata for Japanese subjects (see Section 3.1.1 for strata descriptions).

Subjects will then be randomized at a 1:1:1:1 ratio to receive either MEDI9929 (280 mg [Q2W], 210 mg [Q4W], or 70 mg [Q4W]) or placebo.

Investigational product (MEDI9929 or placebo) must be administered the same day the investigational product is assigned. If there is a delay in the administration of investigational product such that it will not be administered within the specified timeframe, the study monitor must be notified *immediately*.

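### The extended post-dose check covers the first 2 doses in one section and the first 5 in four other places, and the conflict falls on the second drug exposure (Week 4) of both Q4W arms

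*Protocol*

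**What the plan says.** **Length of stay.** Section 4.5.1.3 is the only rule on this: "For the first 2 doses of investigational product, subjects will remain at site for a minimum of 2 hours or until stable, whichever is later". It continues: "For the third and subsequent doses of investigational product, subjects will remain at site a minimum of 1 hour", again extended until the subject is stable. Discharge is the investigator's decision.

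**Vital signs.** Section 4.5.1.3 asks for readings at 60 and 120 minutes after the first 2 doses and at 60 minutes only from dose 3. Four other places ask for 60 and 120 minutes after the first 5 doses and 60 minutes only from dose 6: Section 4.3.3.3, step 15 of the order of assessments in Section 4.2.3, and the vital-sign footnotes to Tables 4.2.2-1 and 4.2.2-2.

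**What counts as a dose.** Section 4.6.1 uses the term for either product: "Investigational product (MEDI9929 or placebo) must be administered the same day the investigational product is assigned". A placebo visit is therefore a dose.

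**What each dose contains.** For the 70 mg and 210 mg arms, Table 3.1.2-1 schedules the MEDI9929 visits as "3 SC injections Q4W from Week 0, Day 1 to Week 48" and the all-placebo visits as "3 SC injections Q4W from Week 2 to Week 50". The note to Figure 3.1.1-1 confirms it: "subjects receiving MEDI9929 Q4W will receive placebo on alternate weeks in order to maintain the blind". The 280 mg arm receives MEDI9929 at every visit from Week 0 to Week 50.

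**Why subjects are watched.** Section 1.5: "Potential risks based on the mechanism of action of MEDI9929 include immune complex disease, serious infections, and hypersensitivity and allergic reactions". Section 5.2 makes anaphylactic reactions an event of special interest that needs rapid reporting.

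**The concern.** Observation after injection is there to catch immediate reactions to the drug, but its length is set by counting injections that may contain none. In the Q4W arms every second administration is placebo, so a count of doses and a count of drug exposures diverge from Week 2 onward.

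Taken alone, that is a feature of a blinded double schedule. It becomes a practical problem because the protocol gives two different counts, and they disagree at doses 3, 4 and 5. At those visits a site following Section 4.5.1.3 may discharge a stable subject after one hour, which makes the 120-minute reading required elsewhere impossible. Dose 3 is also the first re-exposure to MEDI9929 in both Q4W arms.

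Site staff cannot compensate. Those who inject and observe are blinded (Sections 4.5.1.2 and 4.6.2), so they do not know which visit is a re-exposure. What is at stake is how consistently sites observe subjects at that visit, and whether the sponsor knows how many drug exposures its rule covers in each arm.

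**Working it through.** **Step 1: arm size.** Section 4.8.2 raises 124 per arm for a 10% loss of information: 124 / (1 − 0.10) = 137.8, rounded up to 138. Then 4 × 138 = 552. This agrees with Section 4.1.1 ("Approximately 138 subjects will be randomized to each treatment arm") and with Table 3.1.2-1.

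**Step 2: number the administrations.** Dosing is Q2W from Week 0 to Week 50, so dose number = week / 2 + 1. The last dose is 50 / 2 + 1 = 26.

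| Dose | Week | 70 mg and 210 mg Q4W | 280 mg Q2W | 120-min check, Section 4.5.1.3 | 120-min check, the four other places |
|---|---|---|---|---|---|
| 1 | 0 | MEDI9929 (1st) | MEDI9929 (1st) | yes | yes |
| 2 | 2 | placebo | MEDI9929 (2nd) | yes | yes |
| 3 | 4 | MEDI9929 (2nd) | MEDI9929 (3rd) | no | yes |
| 4 | 6 | placebo | MEDI9929 (4th) | no | yes |
| 5 | 8 | MEDI9929 (3rd) | MEDI9929 (5th) | no | yes |
| 6 | 10 | placebo | MEDI9929 (6th) | no | no |

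The minimum stay, set only in Section 4.5.1.3, is 2 hours at doses 1 and 2 and 1 hour from dose 3.

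**Step 3: drug exposures with the 120-minute check.**

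- Section 4.5.1.3 (doses 1 and 2): one in each Q4W arm (Week 0), two in the Q2W arm (Weeks 0 and 2).
- The first-5-doses texts: three in each Q4W arm (Weeks 0, 4 and 8), five in the Q2W arm (Weeks 0 to 8).

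**Step 4: subjects whose second drug exposure falls in the conflict.** In both Q4W arms that exposure is dose 3. Planned subjects: 2 × 138 = 276. Planned active subjects: 3 × 138 = 414. Share of active subjects: 276 / 414 = 66.7%. Share of all randomized subjects: 276 / 552 = 50%.

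In the 280 mg arm the second exposure is dose 2, where all the texts agree. Its third to fifth exposures are the ones in the disputed range.

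**The case against.** The strongest reply is that Section 4.5.1.3 and Table 3.1.2-1 do not conflict. One counts administrations, the other says what each contains, and both can be followed. No passage says that the longer stay was meant to cover two drug exposures. Counting administrations also gives blinded sites a single rule for all arms. The amendment summary gives a reason for limiting the longer stay: no post-dose reactions had been seen in earlier studies. All of this stands. A reader might infer from the table that the observation rule contradicts the dosing schedule, or that a stated intention was missed in the Q4W arms; the protocol supports neither.

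A reader might also infer that reaction rates by dose would not be comparable between regimens. The documents do not support that as a flaw in a planned analysis. Section 4.8.5.1 summarizes adverse events by system organ class, preferred term, severity and relationship, with no by-dose comparison. Adverse events are collected from consent through Week 64 (Section 5.4.1), so a reaction in the second hour is still recorded after the subject has left. At each visit all four arms follow the same rule, so the comparison with placebo is balanced. One hour is a floor, extended until the subject is stable, and treatment for anaphylaxis must be at hand.

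Finally, if the first-5-doses texts govern, Week 4 has its 120-minute check. That limits any claim that Q4W re-exposure goes without it. It does not remove the point, because the protocol does not say which text governs, and the stay rule in Section 4.5.1.3 still allows discharge after one hour at that visit.

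**Conclusion.** The point holds as an internal inconsistency in safety monitoring, with a specific consequence. The protocol requires the 120-minute check at doses 3 to 5 in four places and not in Section 4.5.1.3. The first of the disputed doses is the second MEDI9929 exposure of about 276 of 414 planned active subjects. The two readings cover one against two drug exposures (Q4W against Q2W), or three against five, and neither number is stated anywhere.

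The 67% rests on the planned equal allocation and on no missed Week 2 dose. A Q4W subject who missed Week 2 would receive the second dose at Week 4. The one-against-two figure also depends on Section 4.5.1.3 being the operative text.

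Sample size, type I error and the primary analysis are unaffected, and no planned by-dose safety analysis is affected. The texts should be reconciled. This review takes no position on which of them is clinically right.

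**What to change.** Reconcile Section 4.5.1.3 with Section 4.3.3.3, step 15 of the order of assessments in Section 4.2.3 and the vital-sign footnotes to Tables 4.2.2-1 and 4.2.2-2. Replace the dose counts with named visits, identical in all arms so that the blind holds, for both the longer stay and the 120-minute vital signs. Naming visits also settles what happens after a missed dose. Add a sentence stating how many MEDI9929 exposures those visits cover in the Q4W arms and in the Q2W arm, so that the effect of the alternating placebo is visible. The sponsor's clinical team decides the number of visits and the duration.

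The text change is a few sentences and two footnotes. The operational cost depends on the choice. Each visit named beyond those in Section 4.5.1.3 means a longer stay and one additional vital-sign reading for all subjects, about 552 readings per visit. As a scale only: covering all three disputed doses would mean up to 3 × 552 = 1,656 readings more than Section 4.5.1.3 requires, and none beyond what the four other places already require.
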